5. HOW THE DATA WILL BE COLLECTED OR ACCESSED

Research materials will come from the following sources: Total Cancer Care registry data from the study site, and the Cancer Supportive Care Clinic, part of OSUCCC will be used for recruitment purposes. . Participants' physical function (as measured by the SPPB), muscle strength (handgrip, SPPB), weight, height, and waist circumference will be collected at the in-person meetings (baseline and after the 12-week intervention). Online Research Electronic Data Capture (REDCap)-based questionnaires at baseline and end-of-study will collect assessing dietary quality (DHQIII), self-reported exercise (frequency/duration/intensity), health-related quality of life (RAND-36), and self-efficacy. Basic demographic (e.g., age, race, education) and health characteristics (e.g., comorbidities, stage of cancer at diagnosis, treatments received) will be collected through REDCap questionnaires. These questionnaires will be self-administered and a research assistant will be available to address any technological difficulties. Three months after the 12-week intervention, all participants will return for an in-person assessment of physical function (SPPB), muscle strength (handgrip, SPPB), and health-related quality of life (via REDCap questionnaire).

6. DATA COLLECTION TIMELINE

This is a two-year study. Figure 2, on pages 6 and 7, illustrates the data collection timeline. Briefly, we will recruit 70 participants in 9 months. After recruitment and consent, participants will begin their 12- week intervention. Data will be collected at baseline, end-of-study (12 weeks), and follow-up (3 months after the end of study).

7. HOW THE DATA ARE STORED AND PROTECTED

The proposed intervention utilizes an individualized approach and does not operate in group settings, therefore ensuring participants' privacy. Confidentiality will be protected in several ways. All data points will be collated and stored on a REDCap database, a secure web application. Data will be used only in aggregate and no identifying characteristics of individuals will be published or presented. Confidentiality of data will be maintained by using research identification numbers that uniquely identify each individual. Safeguards will be established to ensure the security and privacy of participants' study records. The information collected from participants in this study has a low potential for abuse, since the data do not address sensitive issues. Nevertheless, appropriate measures will be taken to prevent unauthorized use of study information. All computer systems will be password-protected against intrusion. All network-based communications of confidential information will be encrypted. Data other than demographic information do not use names as an identifier. The research number will be used.

All paper files and computer files with the de-identified data will be stored under lock and key at all times. The files matching participants' names and demographic information with research numbers will be kept in a separate room and will be stored in a locked file that uses a different key from that of all other files. Only study personnel will have access to these files, and they will be asked to sign a document that they agree to maintain the confidentiality of the information. After the study is completed, local data will be stored with other completed research studies in a secured storage vault.

8. WILL DATA BE SENT OUTSIDE OF OSU FOR ANALYSIS?

No.

IV. HUMAN SUBJECTS INFORMATION

1. POTENTIAL RISKS

An adverse event or experience is defined as any health-related unfavorable or unintended medical occurrence that happens during the process of screening or after randomization. Non-serious adverse events are defined as conditions that may be unpleasant and bothersome to the participant, such as sore muscles, that do not require discontinuing the study intervention or terminating components of the intervention. These do not require reporting. Finally, serious adverse events are defined as events that may be harmful to the participant and/or may be serious enough to warrant either temporary or permanent discontinuation of the study intervention, either because they are intolerable or because they are judged to be potentially harmful. All serious adverse events require immediate reporting and an assessment of the implications for the continuation of the study and/or modification of the consent form.

Unexpected adverse events are defined as events that are not listed above potential events and are not listed in the consent form. Monitoring for unexpected serious adverse events attributable to the intervention is the responsibility of the study project manager who is trained and has experience in monitoring and reporting events. The project manager will inform the PI of any events. Specific reporting and review requirements are defined for unexpected events, so that, if an unexpected event is found to be related to the intervention, the protocol and consent can be modified.

On-site adverse events are defined as events that occur at a research study site. Events that require immediate notification of the study PI ([name]) and senior medical oncologist ([name]) and 24-hour notification of the IRB include: (1) deaths, and (2) health events at that result in immediate hospitalization or medical care. These events are also immediately reported to the rest of the study team, the Data and Safety Monitoring Board, and the NIH.

We anticipate that this study will entail minimal physical and psychological risks for study participants. There is a small risk to participants of sustaining an injury while participating in the intervention. However, physical injury is not anticipated and the trained, certified exercise scientist will provide guidance on how to participate in resistance training, safely and effectively. Participant risk may also include, but not anticipated, psychological distress associated with completion of the online questionnaires. If this occurs, study staff will speak to the participant about the difficulties that the questionnaires have caused and will offer a referral to a

mental health professional if necessary. Lastly, we are proposing a synchronous online intervention design to reduce psychological distress and assist with the maintenance of health behaviors among participants.

Potential risks for the registered dietitian and exercise scientist will be minimal. Minor risk, but not anticipated, may include psychological distress associated with potentially negative experiences and feedback from participants (i.e., hard to motivate individuals, reported distressing symptoms). These professionals are from an established programs, experienced in providing guidance and counseling online, and will receive training prior to interacting with the study population.

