As in similar prior lifestyle intervention trials conducted by the study team members, we will obtain a release form from each participant's primary care physician for involvement in the study. We will ask the primary care physicians to complete a form related to the inclusion and exclusion health conditions—yes/no. If an activity-related injury or illness does occur, the PI ([name]), the co-I ([name]), who is an exercise scientist, and study member ([name]), who is a senior oncologist, will be consulted according to the type of symptom reported. In some instances, it may be appropriate to reduce the participant's resistance training goals. If the injury or symptoms do not resolve after an appropriate period of time, the participant will be referred to her primary care provider for further evaluation. The participant will be encouraged to follow the primary care provider's instructions.

After the baseline assessment, participants will be provided (on paper and via email) a weblink to access their REDCap-based weekly logs. The research assistant will provide a demonstration on how to access the REDCap-based logs and enter their weekly dietary intake and exercise adherence. Intervention participants will be advised to contact the research assistant in the event of technical difficulties. Weekly REDCap-based logs of the intervention participant's dietary intake and exercise adherence will offer the registered dietitian and exercise scientist as well as study team insight into their goal progression. These logs will provide an additional method to monitor potential participant difficulties, which the study team will address, therefore, reducing participant risk.

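### No section provides for recording non-serious adverse events or showing harms by arm, and the two arms are observed unequally

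*Combined protocol and SAP*

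**What the plan says.** Section IV.1 (Potential Risks) sorts adverse events into classes. Non-serious events, with sore muscles as the example, are those "that do not require discontinuing the study intervention or terminating components of the intervention. These do not require reporting". Serious events are "events that may be harmful to the participant and/or may be serious enough to warrant either temporary or permanent discontinuation of the study intervention", because they are intolerable or judged potentially harmful. For these the rule is strict: "All serious adverse events require immediate reporting and an assessment of the implications for the continuation of the study and/or modification of the consent form".

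The duty to monitor is narrower: "Monitoring for unexpected serious adverse events attributable to the intervention is the responsibility of the study project manager".

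A further paragraph opens with "On-site adverse events are defined as events that occur at a research study site". It then lists deaths and health events leading to immediate hospitalization or medical care, with notification of the PI, the senior oncologist and the IRB, and adds: "These events are also immediately reported to the rest of the study team, the Data and Safety Monitoring Board, and the NIH".

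The same section expects minimal risk but accepts that "There is a small risk to participants of sustaining an injury while participating in the intervention". Section IV.2 (Protections Against Risk) describes consultation and referral if an activity-related injury or illness occurs. Of the intervention arm's weekly REDCap entries it says: "These logs will provide an additional method to monitor potential participant difficulties, which the study team will address, therefore, reducing participant risk".

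**The concern.** A pilot of resistance training in people aged 65 or over, each with at least one physical function limitation, should tell the next trial how often minor strains, new pain and falls occur. That requires three things: the events are written down, both arms are asked in the same way, and the results are shown by arm. The plan provides for none of these for non-serious events. For serious events it provides reporting but no presentation by arm.

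Without them, the expectation of minimal risk cannot be set against data on non-serious harms. Any comparison put together afterwards would also be distorted, because one arm is seen often and the other is not. Minor events that nobody asked about at the time are hard to recover later.

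**Working it through.** The plan states no harms figure, so there is nothing to reproduce. The check has five steps.

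**1. Where recording could appear**

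- Data to Be Collected: physical function, acceptability, feasibility, strength, diet, exercise, quality of life, self-efficacy, self-regulation, technology competency, anthropometry, and demographic and clinical information. No adverse event item.
- How the Data Will Be Collected or Accessed: the same kinds of measures. No adverse event item.
- Weekly exercise diary (How It Will Be Done): whether the participant exercised, type, intensity and time. No symptom, fall or injury item.
- Process data (Protections Against Risk): visit counts and adherence are the examples given.
- Data Analysis Plan: Aim 1 covers accrual, retention and adherence. Aim 2 covers the SPPB and the other outcomes. No harms analysis, overall or by arm.

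**2. Do the definitions work alike in both arms?**

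The non-serious class, and one limb of the serious class, depend on whether the intervention has to stop. Controls receive only printed survivorship material. A strain that pauses training is serious in the intervention arm. The same strain in a control has no training to pause, and counts as serious only if judged potentially harmful. The monitoring duty for events attributable to the intervention has a similar asymmetry.

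**3. Scheduled contacts between baseline and 12 weeks**

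- Exercise scientist: weeks 1 to 6, then 8, 10 and 12, so 6 + 3 = 9.
- Dietitian: weeks 1, 3, 5, 7, 9 and 11, so 6.
- Intervention arm: 9 + 6 = 15, plus weekly logs (optional social hours not counted).
- Control arm: 0, with no logs.

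**4. Training done without the exercise scientist**

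Participants are encouraged to add two sessions a week, for three in total. Weeks 7, 9 and 11 have no led session, so there are two readings:

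- Three sessions every week: 12 × 3 = 36. Without the exercise scientist: 36 − 9 = 27, and 27/36 = 75%.
- Two additional sessions every week plus the led ones: 12 × 2 = 24, and 24 + 9 = 33. Then 24/33 = 73%.

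**5. What a table could show**

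Inputs are 35 per arm (Sample Size and Justification) and the 80% retention goal. Assuming equal retention, 0.80 × 35 = 28 per arm. With zero events in n, the one-sided 95% upper limit is 1 − 0.05^(1/n):

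- n = 35: 1 − 0.05^(1/35) = 0.082, or 8.2%.
- n = 28: 1 − 0.05^(1/28) = 0.101, or 10.1%.

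The chance of at least one event is 1 − (1 − p)^n. The true rates below are assumed, since the documents give none:

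| n | p = 5% | p = 10% |
|---|---|---|
| 35 | 83% | 97% |
| 28 | 76% | 95% |

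A table by arm would therefore be informative about common harms and would say little about rare ones.

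**The case against.** The strongest reply is that the plan covers the events that matter. The serious class joins its two limbs with and/or, so a potentially harmful event qualifies even if nothing is stopped. All such events must be reported immediately. Every participant has a research number and an assigned arm, so serious events could be counted by arm. This stands, and it rules out three stronger readings that a reader might infer:

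- That the trial cannot describe its safety at all. It can describe serious events, broadly defined.
- That the exemption removes every event that does not stop the intervention. It does not remove events judged potentially harmful.
- That the exempt events are the ones behind drop-out. An event that makes someone stop the intervention because it is intolerable or potentially harmful meets the serious definition. Nothing in the documents links the exempt events to drop-out.

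It can also be said that not reporting is different from not recording, and that in a human-subjects section the word most naturally means notification. That is fair: the text does not forbid recording. But no section provides for it either.

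Finally, a reader might infer that events away from the site escape notification, because that paragraph opens with a definition of on-site events. The documents do not establish this. The sentence listing notifiable events is not expressly limited to the site, the rule for serious events has no location limit, and Protections Against Risk covers any activity-related injury or illness. What remains is unclear wording.

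The figures in steps 4 and 5 give scale and do not measure a defect. Zero events in 35 would not prove minimal risk.

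**Conclusion.** The point holds in a limited form. The plan has no systematic collection of non-serious adverse events and no commitment to present any harms by arm. Its definitions depend partly on stopping an intervention that only one arm receives, and its detection is unequal (15 scheduled contacts plus weekly logs against none over 12 weeks). Followed as written, the pilot cannot describe minor strains, pain, or falls judged neither harmful nor a reason to stop. Nor can it compare harms between arms without ascertainment bias. Serious events are reported and remain countable.

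This rests on the weekly diary containing only the items listed and on no separate adverse event form existing outside these documents. Consent pages are not in the copy reviewed, so what they list could not be considered. The change is worthwhile and inexpensive. It affects neither the sample size nor the efficacy analysis.

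**What to change.** 1. In Potential Risks, state that non-serious events do not require expedited reporting but are recorded.
2. Ask both arms the same short question (injury, fall, new pain, medical care) at the existing 12-week and 3-month visits.
3. Add a descriptive table of non-serious and serious events by arm to the Data Analysis Plan. Use only the answers from these common visits for the between-arm comparison of non-serious events. Anything that surfaces through the logs or online sessions can be listed separately for the intervention arm.
4. Separately, reconcile the wording of the on-site and notification paragraph with the rule that all serious adverse events require immediate reporting, so that its scope is clear.

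The cost is one REDCap item at visits that already take place, one table and a little data entry. No participants or visits are added. One limit remains: people who miss the visits are not asked, which at the 80% retention goal means 70 − 56 = 14 participants at 12 weeks. The table should show how many answered in each arm.

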Resistance training counseling: For the first 6 weeks, the ES will host weekly, one-on-one, 30-minute, online resistance training sessions for the intervention group, using a progression model.⁴⁸ After week 6, the resistance training sessions will taper, and be held biweekly at weeks 8, 10, and 12. Based on behavior change models, at the beginning of all sessions, the ES will review progress toward increased resistance training, and support progress and strategies to overcome barriers through motivational interviewing. In each training session, the ES will provide education, then lead participants through a 5-minute warm-up, followed by a series of whole-body exercises (each major muscle group) performed at each session, and a 5-minute cool-down. The training is based on a co-I's ([name]) expertise in exercise interventions,⁴⁹⁻⁵¹ the ACSM exercise guidelines for cancer survivors,⁵² and ACSM recommendations for progressive resistance training for older adults⁵³ consisting of 1-3 sets of 8-10 exercises with 8-12 repetitions with a 1-2 min rest between sets. Participants will be encouraged to complete these exercises two more times/week, totaling three sessions/week, and record their weekly resistance trainings in the REDCap platform (same weekly log as dietary intake). The diary will ask participants if they exercised (yes/no), type of exercise (i.e., resistance training, walking), intensity (mild/moderate/strenuous) and the time spent exercising for each day of the week. Diaries will be used by the ES to assess exercise adherence and to progress the exercise program during training sessions. Participants will be encouraged to refer to their educational materials for guidance between synchronous resistance training sessions.

Enhanced Control Participants. Participants randomized to the enhanced control group (n=35) will not receive online nutritional or resistance training education or counseling. Control participants will take part in three in-

person assessments (baseline, end-of-study, 3-month follow-up) with study staff and receive printed materials (NCI's "Facing Forward: Life After Cancer Treatment") pertaining to general cancer survivorship.

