- *Self-regulation.* Baseline and end-of-study self-regulation for diet and exercise will be measured by the 12-item Dietary Self-Regulation Scale⁵⁸ and the 12-item Exercise Self-Regulation Scale⁵⁹.
- *Technology competency.* The 8-item eHealth Literacy Scale (eHEALS)⁶⁰ will measure knowledge, comfort, and perceived skills of engaging in eHealth at baseline and end-of-study. A 5-point Likert scale will be used.
- *Anthropometry.* Body weight, height, and waist circumference will be collected at baseline and end-of-study.
- *Demographic and Clinical Information.* Participants' age, race, ethnicity, gender, education, income, marital status, insurance status, cancer diagnosis, stage at diagnosis, time since diagnosis, treatments received (e.g., chemotherapy, radiation) and comorbidities will be collected at baseline and updated at end-of-study.

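### The protocol requires every serious adverse event to be reported, but the only monitoring duty it assigns cannot reach a control participant, and no common enquiry makes ascertainment equal between arms

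*Combined protocol and SAP*

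**What the plan says.** **Potential Risks (section IV.1).** An adverse event is "any health-related unfavorable or unintended medical occurrence that happens during the process of screening or after randomization", with no limit by arm. Serious events are "events that may be harmful to the participant and/or may be serious enough to warrant either temporary or permanent discontinuation of the study intervention". Non-serious events are those that do not call for stopping all or part of the intervention, and they need not be reported. The reporting rule is broad: "All serious adverse events require immediate reporting and an assessment of the implications for the continuation of the study". The duty to look for events is narrow: "Monitoring for unexpected serious adverse events attributable to the intervention is the responsibility of the study project manager". The next sentence is broad again: "The project manager will inform the PI of any events". Deaths, and events leading to immediate hospitalisation or medical care, go at once to the principal investigator and the senior oncologist, and within 24 hours to the IRB. That rule states no arm limit, but its paragraph opens by defining events that happen at a study site.

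**How It Will Be Done (section III.2).** Intervention participants have individual dietitian and exercise sessions over 12 weeks. Controls "will not receive online nutritional or resistance training education or counseling"; they attend at baseline, end-of-study and 3 months.

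**Protections Against Risk (section IV.2).** The weekly logs kept by intervention participants are named as a further way to notice difficulties. The dietitian and exercise scientist are trained in participant safety and have designated contacts for concerns.

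**Data to Be Collected (section 4).** No adverse-event item is listed. Treatments received and "comorbidities will be collected at baseline and updated at end-of-study". The 3-month visit covers SPPB, handgrip and health-related quality of life.

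**The concern.** A reporting rule acts only on events that staff come to know about. Here the stated search for serious events is confined to those judged attributable to an intervention that one arm does not receive, and the frequent contacts through which events would surface also belong to one arm. The same fracture or hospital admission is then more likely to be recorded in the intervention arm than in the control arm.

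At stake is the use of the control arm as background. In adults aged 65 and over some serious events will occur regardless of the programme. If they are sought in one arm and met by chance in the other, the intervention can look more harmful than it is. If attribution is settled before an event is recorded, an event that looks unrelated case by case may never enter the by-arm counts, where an excess over control could show.

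**Working it through.** The plan states no safety figure to reproduce, so the check is a comparison of rules, a count of contacts and an illustration.

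**1. The rules in Potential Risks side by side**

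| Rule | Limited by arm or attribution? | Can it reach a control? |
|---|---|---|
| Adverse-event definition | No | Yes |
| Serious: potential harm to the participant | No, but names no outcome | Yes |
| Serious: may warrant stopping the intervention | Tied to the intervention | No |
| Serious/non-serious boundary | Refers to stopping the intervention | Not in a meaningful way |
| Reporting of all serious events | No | Yes, once known |
| Assigned monitoring duty | Unexpected and attributable only | No |
| Death/hospitalisation notification | No | Yes, but reach to events at home unclear |

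The reporting rule and the monitoring duty therefore differ in scope within one section.

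**2. Scheduled one-on-one contacts from baseline to week 12 (section III.2)**

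- Dietitian, weeks 1, 3, 5, 7, 9, 11: 6.
- Exercise scientist, weekly in weeks 1 to 6: 6; then weeks 8, 10, 12: 3. Subtotal 6 + 3 = 9.
- Intervention arm: 6 + 9 = 15, plus weekly logs and three optional social hours.
- Control arm: none described between the baseline and end-of-study visits.

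**3. Contacts common to both arms after baseline**

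There are two: end-of-study and 3 months. The first updates comorbidities and treatments. The second has no stated clinical update. Neither has an adverse-event question.

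**4. Illustration (assumed values only)**

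The documents give no event rate and no capture rate. Assume the same true risk r in both arms, full capture in the intervention arm and a fraction q captured in controls. Expected recorded events are 35 × r against 35 × r × q.

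| r | Intervention | Control, q = 0.50 | Control, q = 0.75 |
|---|---|---|---|
| 5% | 1.75 | 0.88 | 1.31 |
| 10% | 3.5 | 1.75 | 2.62 |
| 20% | 7.0 | 3.5 | 5.25 |

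An apparent difference can arise with no true one. The table shows the mechanism; it does not estimate its size in this trial.

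**5. What 35 per arm could show with equal capture**

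Assume a 10% control rate and a two-sided Fisher's exact test at 0.05. Power is about 13% against 20%, 46% against 30% and 78% against 40%. Only a very large excess would be detected, so any by-arm summary is descriptive.

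**The case against.** The strongest reply is that the section already covers controls. It requires all serious events to be reported, has the project manager tell the principal investigator of any events, gives potential harm as a separate route to seriousness, and notifies deaths and hospitalisations without an arm limit. This stands against three readings that the narrow monitoring sentence invites:

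- *That control events fall outside the safety rules.* They fall within the reporting rule; only the assigned monitoring duty misses them.
- *That seriousness depends wholly on stopping the intervention.* The two limbs are joined by and/or, and a control participant's fracture can meet the first.
- *That the project manager screens events for attribution before the investigator hears of them.* The text does not say so, and the sentence on informing the investigator points the other way.

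It is also fair to say that participants are not left unexamined after week 12: everyone returns in person at 3 months and completes the quality-of-life questionnaire. What is missing is an adverse-event or clinical update. Scheduled sessions end at week 12, so the later period is a gap in both arms and not evidence of imbalance. Some control events would surface at the end-of-study visit, so zero capture in controls is not a reasonable assumption.

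Finally, the Data Analysis Plan contains no between-arm safety comparison, so no planned test is biased. That limits the point to whatever description of serious events is eventually given. None of these replies supplies a means, equal in both arms, of learning that an event has happened.

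**Conclusion.** The point holds in a limited form. Potential Risks pairs a broad reporting rule with a monitoring duty that cannot apply to controls, and the two must be reconciled. Part of the seriousness definition refers to an intervention that controls do not receive, and the other part names no outcome. Whether the death and hospitalisation rule covers events at home is unclear. With 15 scheduled sessions plus logs against no scheduled control contact between baseline and week 12, and no common enquiry at either later visit, serious events would be ascertained unequally.

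The contact count is firm, as far as the documents describe contact. The effect on event counts is unknown because it depends on event and capture rates that the documents do not give. A reader might infer that the trial's safety conclusions are invalid, or that correcting this would let the pilot detect an excess of harm. Neither follows: no safety test is planned, and 35 per arm could not support one for modest differences. This is a worthwhile, inexpensive correction; it does not threaten the trial's main aims.

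**What to change.** In Potential Risks:

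- Make the monitoring duty match the reporting rule: all serious adverse events, in both arms, whether they occur on-site or off-site.
- State seriousness in terms that do not depend on receiving the intervention.
- Record the event first and judge relatedness afterwards.
- Say explicitly whether the death and hospitalisation notification applies to events away from a study site.

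In Data to Be Collected, add one short question, identical in both arms, at the existing end-of-study and 3-month visits, for example on hospitalisation, injurious fall and fracture since the last visit. In the Data Analysis Plan, state that any by-arm summary of serious events uses those common contacts and is descriptive. Events learned of through sessions or logs would still be reported, but listed separately from that summary.

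The cost is protocol wording, one REDCap form, a few minutes per visit and a few more unrelated events to log among 70 participants. A common question removes much of the imbalance but not all of it, since recall at 12 weeks may differ between people who have been asked weekly about their progress and people who have not.
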